4.2 Pre-Treatment Phase (Screening)

At screening, the investigator or his/her designee will assign a unique number to patients being considered for the study, as outlined in the 7904 Manual of Procedures. The patient/parent must provide a signed Informed Consent Form prior to any study screening evaluations being performed. Once the patient/parent provides a **signed informed consent form** and **eligibility is confirmed (all inclusion/exclusion criteria have been verified)**, the investigator or his/her designee will register the patient for randomization.

Screening evaluations will include demography, relevant medical history/current medical conditions, a physical examination (including a neurological examination), suicidal ideation/behavior assessment, vital signs, laboratory assessments, and other additional study entry evaluations. Primary endpoint neurocognitive data will be collected for screening purposes (SB-5, CPT-3, and Purdue Pegboard Test). Once the patient is confirmed as being eligible to be randomized, the baseline visit will be scheduled to occur within 6 weeks of the screening visit.

Participants will be screened for signs and/or symptoms of cancer. If a patient presents at the screening visit with a mass that may be malignant or benign, the study physician will refer them to the appropriate health care providers. If the mass is benign, and the patient meets all other inclusion/exclusion criteria, the patient may be enrolled in the study. Additional information about cancer screening can be found in the Manual of Procedures.

Participants will be screened for suicidal ideation and/or behaviors using the Columbia Suicide Severity Rating Scale (C-SSRS). Participants that are determined to have significant suicidal ideation and/or behaviors, as

defined in Section 4.6.5, will be ineligible to participate in the trial, and will be referred to the appropriate healthcare provider per the principal investigators discretion.

A complete list of screening evaluations is provided in the schedule of evaluations. All of the above assessments/procedures must be conducted and evaluated prior to randomization.

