4.3 Blinded Treatment Phase

All baseline procedures and evaluations should be completed within 6 weeks of the screening visit. If a patient's safety lab results are out of range, and the investigator has reason to believe there were situational factors affecting the values, the screening labs may be repeated. The safety evaluations may be completed at a lab that is geographically close to the participant and either provide the results of that analysis directly to the study team, or a sign a release so the study team can obtain the results from the lab. If a patient's baseline visit is more than 6 weeks after the screening visit the participant must have the safety labs re-drawn and processed, have the physical and neurological exam re-done, and the study team will confirm that there are no changes in the medical history or changes to the patient's current medications. If the screening safety evaluation and/or lab results are out-of-range, the participant will not be eligible to participate in the study. Patients who meet the study eligibility criteria following screening will be randomized to receive everolimus or placebo. The randomization ratio is 1:1, with one patient being randomly assigned to everolimus for every one patient randomly assigned to placebo. Treatment assignment via the RDCRN Members' Website should occur prior to the Baseline visit to allow adequate time for pharmacy preparation. Patients must start treatment within 7 days of the baseline visit, given that the participant still meets all inclusionary criteria and has not developed any exclusionary criteria. The medication should be taken at the same each day with a light, low-fat breakfast (i.e. 8:00 am with light breakfast).

The duration of blinded phase this study is 6 months. Patients will have their first daily dose of everolimus or placebo within 7 days of Visit 2 (baseline) and will continue on treatment for 6 months unless an intolerable toxicity occurs, withdrawal of consent, or investigator decision to discontinue the patient from study treatment.

Starting dose and adjustments are defined in Section. 6.2.

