Social Responsiveness Scale, Second Edition (SRS-2): Total T-score

Repetitive Behavior Scale - Revised (RBS-R): Total raw score

Improving Associated Behaviors

Behavior Rating Inventory of Executive Function (BRIEF): General executive composite and sub-scale scores Adult/Child Behavior Checklist (CBCL ARF/CBCL): Total problems T score Short Sensory Profile (SSP): Total Score

Improving Adaptive Behaviors

Vineland Adaptive Behavior Scales-III (VABS-III) Caregiver report: Composite and scale scores.

A measure of functional adaptive behavior, i.e. ability to cope with personal and social skills in everyday life that may be deficient in autism or developmental delays. Tester completes a questionnaire through interview with parent or caregiver. Any age. No parallel forms. Outcome measures: raw scores converted to scaled scores, then a summary value for a number of domains.

Table 11 Neuropsychological Assessments Timeline

Instrument	Information Source	Screening (Visit 1)	Baseline^ (Visit 2)	3-month [#] (Visit 5)	6-month [#] (Visit 8)
Primary Efficacy Outcome Neurocognitive Composite	Testing		Х	Х	Х
Stanford-Binet Fifth Edition (SB-5) / Mullen Scales of Early Learning (MSEL)	Testing	Х			х
Columbia-Suicide Severity Rating Scale	Interview	Χ		X	X
Stanford-Binet Working Memory Subscale Only	Testing		Х	X	
Conners' Continuous Performance Test (CPT-3/K-CPT-2)	Testing	X	х	x	x
Wechsler Processing Speed Index (PSI)	Testing		X	X	X
Wide Range Assessment of Memory and	Testing		Х	X	X

Learning-2 (WRAML-2)					
Peabody Picture Vocabulary Test – Fourth	Testing		X	X	x
Edition (PPVT-4)			^	^	^
Expressive Vocabulary Test – Second	Testing		X	X	x
Edition (EVT-2)					
Purdue Pegboard (PP)	Testing	Χ	X	X	X
Autism Diagnostic Observation Schedule (ADOS-2)	Observational		Х		X
Social Responsiveness Scale – Second	Parent/Caregiv				
Edition (SRS-2)	er/Informant or		X	X	X
	Self- Report				
Repetitive Behavior Scale – Revised (RBS-	Parent/Caregiv				
R)	er/Informant or		X	X	X
	Self Report				
Developmental Coordination Disorder	Parent/Caregiv				
Questionnaire (DCDQ)	er/Informant or		X	X	X
	Self Report				
Behavior Rating Inventory of Executive	Parent/Caregiv				
Function (BRIEF)	er/Informant or		X	X	X
	Self Report				
Adult/Child Behavior Checklist (CBCL	Parent/Caregiv				
ARF/CBCL)	er/Informant or		X	X	X
	Self Report				
Short Sensory Profile (SSP)	Parent/Caregiv				
	er/Informant or		X	X	X
	Self Report				
Vineland Adaptive Behavior Scales (VABS-	D 110				

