In objective 2, we will examine whether the everolimus group will show more improvement, compared to the placebo group, on the main neurocognitive efficacy composite outcome. Randomization Group (everolimus versus placebo) differences on the neurocognitive composite will be analyzed using mixed effects (growth curve) modeling, fully utilizing repeated measurements collected at three points (Time: baseline, 3-month follow-up, and 6-month follow-up). A significant interaction between Time and Randomization Group, with the everolimus group showing a more favorable outcome trajectory, will support the primary efficacy hypothesis. Maximum likelihood estimation will be implemented in the Mplus program version 7.2 or above.

Mixed effects (growth curve) model analyses will be conducted following the intention-to-treat principle. Data points that are missing due to subject attrition will be handled assuming that data are missing at random (MAR) conditional on observed information, which is less restrictive than missing completely at random (MCAR) assumed in fixed effects analyses such as ANCOVA and regression analysis. In this procedure, all available cases including the ones with missing information will be included in the analyses. By including every subject who completed at least one assessment, we are not only more likely to conserve power, but also less likely to produce biased effect estimates. In mixed effects analyses, the slope of the outcome will be modeled as the key

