dependent variable predicted by randomization group. We will conduct the analysis with and without conditioning on relevant baseline covariates. The results of these longitudinal analyses can be easily converted to a cross-sectional group effect at each assessment time point to describe the magnitude and significance of group differences. Of particular interest is the group difference at end of treatment (6-month assessment). The mixed effects analyses will be repeated using a model where the baseline scores on each outcome are treated as a baseline covariate to control for (instead of as a part of) the repeated measures. This model can be useful if there is a considerable heterogeneity between before and after treatment processes. We will also analyze the data using conventional ANCOVA treating the end point neurocognitive composite as the dependent variable and controlling for the baseline neurocognitive composite. Further analyses will be conducted using the same analysis models but with transformed data (e.g., log transformation) to check the sensitivity of the results to deviation from outcome normality. Statistical significance of all main effects and interaction terms as well as cross-sectional group differences will be determined using a one-tailed Type 1 error rate of α =.05. The same analysis strategy will be employed for secondary efficacy outcomes and a false discovery rate correction will be implemented to control inflation of Type 1 error.

If the exploratory biosample objectives are pursued, we will explore whether baseline peripheral blood levels of PTEN-associated pathway molecules (PI3K/AKT, mTOR, MAPK protein levels) change with treatment and if changes in peripheral pathway molecules correlate with clinical improvement. To determine whether PTEN-associated pathway molecules change with treatment, we will use a similar mixed effect (growth curve) modeling approach to that described above for Secondary Objective with screening, 3-month, and 6-month pathway measurements as outcome measures. The Time by Randomization Group interaction will test whether the everolimus treatment group shows improvement/normalization of PTEN-pathway molecule levels relative to placebo. This component will be dependent on securing additional funds.

In analyzing the resting state EEG and AEP data we will focus on the following:

- 1. Baseline EEG gamma power
- 2. AEP N1 habituation

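### The three core tests are scheduled twice before dosing, but the named efficacy models use only the baseline score. Prespecifying the screening score would cost little and probably add some precision.

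*Combined protocol and SAP*

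**What the plan says.** Protocol section 4.2 has the core tests done at the screening visit: "Primary endpoint neurocognitive data will be collected for screening purposes (SB-5, CPT-3, and Purdue Pegboard Test". Tables 11 and 13A then repeat the CPT and the Purdue Pegboard at baseline. For working memory, the full SB-5 (or Mullen) is given at screening, and the row labelled "Stanford-Binet Working Memory Subscale Only" is marked at baseline and Month 3. Section 4.3 sets the spacing: "All baseline procedures and evaluations should be completed within 6 weeks of the screening visit". Sections 4.3 and 7.7.1 put the first dose within 7 days of the baseline visit, and sections 4.3 and 7.5 place treatment assignment before that visit.

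For efficacy, section 17 specifies a growth model "fully utilizing repeated measurements collected at three points (Time: baseline, 3-month follow-up, and 6-month follow-up". The Time by Group interaction in this model is the test of the efficacy hypothesis. A second mixed model treats the baseline score as a covariate, and an ANCOVA compares endpoint composites "controlling for the baseline neurocognitive composite". Section 17.1 repeats the same three time points in its power argument. Beyond that the text is open: "We will conduct the analysis with and without conditioning on relevant baseline covariates". No efficacy covariate is named there. Screening values do serve as an analysis time point in section 17, but only for the PTEN-pathway molecules.

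**The concern.** A single pre-treatment score carries visit-to-visit noise, and that noise passes into any change, slope or baseline-adjusted comparison. Here a second pre-dose measurement of the same three constructs is already scheduled, normally within six weeks of the first. It is also the only core score obtained strictly before randomisation. The plan uses it for eligibility and gives it no stated role in the efficacy analysis.

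Precision matters in this trial. Randomisation is capped at 40. Section 17.1 concedes power of only .65 for an endpoint comparison at 0.65 SD, the difference it calls clinically meaningful. The composite result also decides whether this outcome is a candidate for Phase III. If use of the screening score is not fixed before unblinding, adding it later would look like a choice made on the results.

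**Working it through.** **Inputs.** From section 17.1: 20 per arm, one-sided α=.05, target difference 0.65 SD, and correlation between repeated measures r≥.30 (the only correlation given). From section 17: visits at 0, 3 and 6 months. Assumptions: unit variance at each visit, complete data, and r up to .80 to show a range.

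**1. The plan's own figures.** The noncentrality is d×√(20/2). At d=0.80 it is 2.530, and the noncentral t with 38 df gives power .799 (plan: .80). At d=0.65 it is 2.055, giving .646 (plan: .65). The plan's .83 at 0.50 SD is reproduced as .827 by a 2-df interaction F-test with f=.25 and λ=40×3×.25²/.70=10.71. That is an omnibus test, so it is not the comparator for the one-sided slope test below.

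**2. ANCOVA, equal correlations.** Residual variance is 1−r² with baseline alone and 1−2r²/(1+r) with screening added. With equal correlations, a separate covariate and a mean of the two give the same result. Power is at 0.65 SD, with 37 df before and 36 after.

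| r | baseline only | plus screening | cut | power |
|---|---|---|---|---|
| .30 | .910 | .862 | 5.3% | .681 → .701 |
| .50 | .750 | .667 | 11.1% | .753 → .795 |
| .70 | .510 | .424 | 17.0% | .881 → .927 |
| .80 | .360 | .289 | 19.8% | .957 → .982 |

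**3. Slope and change tests, equal correlations.** Measure time in units of 6 months with a random intercept. The slope variance is (1−r)/S, where S is the sum of squared deviations of the visit times.
- Times 0, .5, 1: S=.50, so the variance is 2(1−r).
- Times 0, 0, .5, 1 (mean .375): S=2×.1406+.0156+.3906=.6875, so the variance is 1.4545(1−r).
- Cut: 1−.50/.6875=27.3% at any r.

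A generalised least squares calculation for both arms, with a screening-visit effect common to the arms, gives the same 27.3%. Power at 0.65 SD goes from .524 to .639 (r=.30), .646 to .765 (r=.50) and .832 to .921 (r=.70). If true slopes also vary between patients the cut is smaller: at r=.70, 23.4% with slope variance .1 and 18.2% with .3. For a simple change score the variance goes from 2(1−r) to 1.5(1−r), a cut of 25%.

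Screening must be coded as time 0 here. Coding it six weeks before baseline on the treatment slope produces an apparent cut of 45.8%, but only by letting the arms diverge before dosing.

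**4. Unequal correlations (illustrative assumptions).** Write r1 for baseline–Month 6, r2 for screening–Month 6 and r0 for screening–baseline.
- Separate covariate: residual variance 1−(r1²+r2²−2·r1·r2·r0)/(1−r0²).
- Mean as covariate: 1−(r1+r2)²/[2(1+r0)].
- Change from the mean: 1+(1+r0)/2−(r1+r2), against 2−2·r1 for baseline only.

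| r1 / r2 / r0 | baseline only | separate | mean | change score |
|---|---|---|---|---|
| .70/.65/.75 | .510 | .474 (−7.0%) | .479 (−6.0%) | .600 → .525 (−12.5%) |
| .60/.50/.70 | .640 | .627 (−2.0%) | .644 (+0.6%) | .800 → .750 (−6.3%) |
| .70/.60/.80 | .510 | .506 (−0.9%) | .531 (+4.0%) | .600 → .600 (0%) |

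For the growth slope with the visit effect, let correlation be c×b^t, with t the gap in 6-month units and screening .25 before baseline. The cut is 17.7% at c=.8, b=.9 and 7.5% at c=.9, b=.8.

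**The case against.** A scheduled baseline is a standard and valid pre-treatment value, and section 17 describes the trial as exploratory and mainly descriptive. Nothing in the plan is biased or unanalysable on this account. The clause allowing relevant baseline covariates could admit screening scores. All of this stands, except that an open clause does not prespecify their use.

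A reader might infer that the plan gives up a fixed and certain saving, for example 11 to 25% of error variance. The documents do not support that. The 11% needs r=.50 in the ANCOVA, and the 25% is the change-score result; both assume equal correlations. At the documents' own r=.30 the ANCOVA cut is 5.3%. Screening and baseline are close together while Month 6 is far from both, so some decay of correlation with time is plausible and shrinks the gain.

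A reader might also infer that the two scores should simply be averaged, or treated as interchangeable time-0 observations. Step 4 shows that an average can raise the variance. Eligibility requires a below-mean score on at least one core test, so regression to the mean and practice effects are expected between the visits. They affect both arms and do not bias the comparison, but a common time-0 mean would not fit. A visit effect deals with this and, with equal correlations, costs no precision.

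Finally, not every patient will have two comparable core sets. Section 4.6.1 requires only one of the three tests, the Wechsler substitute is not scheduled at screening, and the note to Table 11 allows natural-history scores from within 6 months to be reused. This limits the gain but does not remove the case.

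**Conclusion.** The point holds as a worthwhile, low-cost improvement to prespecify; it is not an error that invalidates the plan. The double pre-dose testing and the baseline-only models are both explicit in the protocol.

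Under equal correlations, the gain is about 5 to 20% of ANCOVA error variance for r from .30 to .80, and about 25 to 27% of the variance of the change or slope test. The slope figure matters more, because the Time by Group interaction is the stated test of efficacy. If correlation decays with time the gain is smaller, and for ANCOVA it can be near zero (0.9% in one case above). These figures assume complete data and the core composite. For the second version of the composite, which Table 12 lists as the primary efficacy outcome, only the core part has two pre-dose scores, so its gain is smaller.

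**What to change.** In section 17:

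- Compute the core composite at screening by the same rules as at baseline, and state when the two count as comparable (same component tests; how reused natural-history scores are handled).
- In the ANCOVA and the baseline-as-covariate mixed model, add the screening composite as a separate second covariate, not as a forced average. State how a missing screening composite is handled, so that no randomised patient is dropped for lack of it.
- In the growth model, enter screening as an additional pre-dose observation at time 0, with a screening-visit fixed effect common to both arms.
- Keep the baseline-only version of each model as a sensitivity analysis.
- Finalise this before unblinded data are analysed.

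The cost is some analysis-plan wording, a few lines of code and one extra term in each model. It needs no new visits or tests.

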Secondary Objective – Efficacy. For power estimation purposes, the variability in PTEN patients treated with an mTOR inhibitor is expected to be similar to the untreated sample. Preliminary data indicates that the measures which comprise the dominant portion of the neurocognitive composite index (processing speed working memory, and fine motor) are highly sensitive to the brain dysfunction seen in PTEN patients with ASD. The effect sizes are approximately 1 SD or larger. In a comparison between mTOR treated vs. untreated PTEN patients, an effect size of at least 0.65 SD would be of interest and represent clinically- meaningful improvement. For example, an effect size of at least 0.65 SD on cognitive measures would translate to a 10-point standard score improvement in the everolimus-treated group relative to placebo. An improvement of 10 or more points is outside the standard error of measurement for most cognitive measures and is typically considered a reliable change when disordered populations are re-tested.

A sample size of 40 (20 per arm) patients will permit detection of endpoint (6-month follow-up) differences of at least 0.80 SD at the 5% significance level (one-sided alpha = 0.05) with 80% power (1- β). Statistical power will be weaker (1- β =.65) if smaller cross-sectional differences are observed (0.65 SD). However, statistical power is very strong, even for smaller differences (Cohen's d≥.50 equivalent to ≥.50 SD difference) when the full repeated measures nature of the design is considered – baseline, 3-month follow-up, 6-month follow-up. Assuming even modest correlations between repeated measurements of outcome variables (r≥.30), power to detect clinically meaningful differences of .50 SD is very good (1- β =.83; one-sided α =.05). If the primary outcome measure (neurocognitive composite) meets nominal statistical significance in the expected direction (one-tailed p<.05) or a secondary outcome measure meets a more stringent false discovery rate-corrected

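### If group may shift the intercept, the lead Time-by-Group slope test is in effect an unadjusted change-score comparison, less precise than a baseline-adjusted Month 6 contrast

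*Combined protocol and SAP*

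**What the plan says.** Section 17 (objective 2) analyses the neurocognitive composite with a mixed effects growth-curve model using "repeated measurements collected at three points (Time: baseline, 3-month follow-up, and 6-month follow-up". Baseline is therefore one of the outcomes. The decision statement is: "A significant interaction between Time and Randomization Group, with the everolimus group showing a more favorable outcome trajectory, will support the primary efficacy hypothesis". The estimand is a single slope: "In mixed effects analyses, the slope of the outcome will be modeled as the key" dependent variable, with randomised group as its predictor.

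The same section adds: "Of particular interest is the group difference at end of treatment (6-month assessment"). It lists two baseline-adjusted analyses after the lead one. The first is a repeat of the mixed model: "The mixed effects analyses will be repeated using a model where the baseline scores on each outcome are treated as a baseline covariate". The second is a "conventional ANCOVA treating the end point neurocognitive composite as the dependent variable and controlling for the baseline neurocognitive composite".

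Two things are left open. The section does not say whether group has an effect on the intercept, that is, whether the arms' baseline means may differ in the model. The nearest indication is "Statistical significance of all main effects and interaction terms as well as cross-sectional group differences will be determined using a one-tailed Type 1 error rate", which suggests a group main effect without stating one. It also gives no covariance structure. Section 17.1 makes the composite a Phase III candidate if it reaches one-tailed p<.05, without saying which of these models supplies the p-value.

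**The concern.** A straight line through three equally spaced visits takes its slope from the first and last. If the model also lets each arm have its own baseline mean, the lead test becomes a comparison of raw change from baseline. That fixes the coefficient on baseline at 1, whatever the correlation, whereas a baseline-adjusted analysis uses the best coefficient. The Month 6 difference implied by such a model would also carry any chance imbalance at baseline, and Section 7.5 stratifies randomisation by age only.

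At stake is precision in a trial of 40 patients. The plan already collects the baseline and already lists adjusted models, but the test that leads may be the one that uses the baseline least well.

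**Working it through.** **Inputs.** Visits at 0, 3 and 6 months (Section 17); 20 per arm, one-sided alpha .05, Month 6 effects of 0.80 and 0.65 SD, r of at least .30 (Section 17.1). SD is set to 1. The correlation r between baseline and Month 6 is an assumption, shown from .3 to .9.

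**The plan's own figures.** Section 17.1 states: "A sample size of 40 (20 per arm) patients will permit detection of endpoint (6-month follow-up) differences of at least 0.80 SD" with 80% power, and .65 power at 0.65 SD. A two-sample noncentral t with 38 df gives .799 and .646, so both reproduce as unadjusted Month 6 comparisons. The .83 quoted for 0.50 SD reproduces (.827) as a 2-df omnibus interaction F test with f=0.25, r=.30 and three visits. That is not the 1-df slope test, so it does not bear on the comparison below.

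**Slope weights.** The least-squares weights are (t - 3)/18 at t = 0, 3, 6, that is (-3, 0, 3)/18. Multiplied by 6 months they are (-1, 0, +1). Generalised least squares gives the same weights under compound symmetry, AR(1), and random intercept plus slope with equal residual variances, when group is in the intercept and data are complete.

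**Variances of the Month 6 treatment difference, n=20 per arm.**
- Slope x 6, group in the intercept: 2(1-r) x 2/n.
- Baseline-adjusted Month 6 contrast: (1-r^2) x 2/n.
- Ratio adjusted/slope: (1-r)(1+r) / [2(1-r)] = (1+r)/2.

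Power below is at 0.65 SD by noncentral t. The adjusted analysis is charged one degree of freedom and a small-sample factor of 1+1/36.

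| r (assumed) | Slope variance | Adjusted variance | Ratio | Power, slope | Power, adjusted |
|---|---|---|---|---|---|
| .3 | .140 | .091 | .65 | .52 | .67 |
| .5 | .100 | .075 | .75 | .65 | .74 |
| .7 | .060 | .051 | .85 | .83 | .87 |
| .8 | .040 | .036 | .90 | .94 | .95 |
| .9 | .020 | .019 | .95 | .998 | .998 |

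An unadjusted Month 6 comparison has variance 2/20 = .100. Below r=.5 the slope test is therefore less precise than ignoring baseline altogether.

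**Simulation.** In 20,000 trials with a true 0.50 SD effect, variances (slope vs adjusted) were .141 vs .093 at r=.3 and .060 vs .052 at r=.7. Power was .37 vs .48 and .64 vs .69.

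**Group not in the intercept.** With equal baseline means and a linear effect x = (0, .5, 1), the variance is (2/n)/(x'V⁻¹x). At r=.5 under compound symmetry, x'V⁻¹x = 2(1.25 - .25 x 2.25) = 1.375, so the variance is .100/1.375 = .0727, against .0750 for Month 6 ANCOVA. At r=.3 it is .0845 vs .0910; at r=.7, .0505 vs .0510. This slope test is baseline-adjusted and Month 3 contributes.

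**Incomplete data and unequal variances.** With 10% dropout and group in the intercept, slope variance is .1497 at r=.3 and .1078 at r=.5. The Month 6 contrast with equal baseline means gives .1008 and .0828 (ratios .674 and .769). With unequal residual variances over time, Month 3 weights ran from about -.33 to +.29, and the ANCOVA/slope ratio stayed between .76 and .92.

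**The case against.** The strongest reply is that the plan never says group enters the intercept. Read literally, group predicts the slope. If it predicts nothing else, baseline means are equal across arms and the lead test is already adjusted, with slightly better precision than Month 6 ANCOVA. The reference to main effects covers every model in that paragraph and might mean Time. This stands as a condition on the whole point. It does not remove it: a main effect of group is the ordinary companion of a Time-by-Group interaction, and if equal baseline means are intended the plan should say so.

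Second, zero weight for Month 3 needs complete data and a time-symmetric covariance, while Section 17.1 expects about 10% dropout and Section 17 uses all available cases. This also stands, although the adjusted contrast remained more precise in each case checked.

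Third, r may be high. Section 17.1 treats a 10-point change as usually reliable. If that means a 90-95% reliable-change criterion with SD 15 (an assumption), r would be about .92 to .94 and the gain negligible. A one-standard-error reading implies only r of at least .56. The size is therefore uncertain.

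Fourth, moving to baseline as a covariate would drop patients without a post-baseline score, against the stated aim of including everyone with at least one assessment. This stands against that remedy, but not against constraining the baseline means.

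Finally, efficacy is secondary, the trial is exploratory, and adjusted models are already listed. That limits the consequence, but Section 17.1 still lets one p-value, from an unnamed model, select the composite for Phase III.

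**Conclusion.** The point holds conditionally. If group may shift the intercept, the lead slope test is with complete data and a time-symmetric covariance an unadjusted change-score test, and it loses precision against an adjusted Month 6 contrast by the factor (1+r)/2 under equal variances. The loss is material at r=.3 to .5, small at .7 to .8, and essentially nil from .9.

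A reader might infer three stronger things that the documents do not support. One is that Month 3 is wasted whatever the model: the intercept specification and covariance are not given, and dropout or unequal variances give Month 3 some weight. Another is that the trial forfeits a quarter of its patients: that is the ratio at r=.5 only, and the documents give no value of r beyond a lower bound. The third is that the slope test is biased or invalid: under randomisation it is valid, only less efficient.

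**What to change.** In Section 17, name one lead efficacy test: the Month 6 treatment difference from the planned repeated-measures model, with baseline kept as an outcome and baseline means constrained equal across arms (no group effect at baseline). This adjusts for baseline and keeps every patient with at least one assessment. State the covariance structure, and whether time is linear or categorical. Keep the unconstrained slope interaction, the baseline-as-covariate mixed model and the ANCOVA as supportive. In Section 17.1, tie the one-tailed p<.05 rule to the lead test.

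The cost is wording only, and at most about one degree of freedom. No visits, measures or patients are added.
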